9.4 Secondary Analysis Methods

The mean change from baseline in UDI-irritative and UDI-stress scores at 1 year will be compared between groups using the same analysis methods described for the primary analysis. If the difference is statistically significant, the potential clinical significance of the difference will be discussed. Additional analyses will be conducted to determine whether the MIDs in this MUI population differ from previously published MIDs.

9.5 Other Analysis Methods

9.5.1 Other UUI/OAB Outcomes

Bladder diary

We will compare change in number of urge IEs and urgency-episodes and nocturia episodes between groups from baseline to 6 and 12 months. Of note, not all four symptoms of OAB (frequency, urgency, nocturia, and UUI) are required to be present at baseline for eligibility into this trial (only UUI required). Changes from baseline in bladder diary outcomes will be calculated and analyzed using the methods described for the analysis of the primary outcome.

For urinary frequency, women reporting on average >8 voids/24 hours at baseline will be considered symptomatic, and normalization of voiding frequency will be defined as < 8

voids/24 hours at 1 year. A 50% improvement will be defined as a reduction by half in the number of voids that patients had at baseline. The number of women who had normalization of voiding frequency and 50% improvement will be compared between groups separately and collectively. We will also assess the proportion of women who had worsening of urinary frequency (includes women who developed de novo frequency and those who worsened). These dichotomous outcomes will be analyzed using logistic regression, controlling for the design effects of stratification by center and by baseline urge IE group. To assess the impact of additional treatment prior to 1 year, sensitivity analyses will be conducted in which women who request additional treatment will be assigned the less-favorable outcome.

OAB-SAT-q and OAB-q

For these scales and associated subscales, differences from baseline will be calculated for the OAB-q, and methods described for analysis of the primary outcome will be used to test for differences between treatment groups at 12 months. For the OAB-SAT-q, differences in post-treatment scores will be compared between groups.

The scoring manual for the OAB-SAT-q states that higher scores should correspond to better outcomes and also details that final composite scores for each dimension should be obtained by subtracting raw scores from the highest possible score and dividing by range. However, based on the direction of score for individual responses, this derivation would result in lower scores corresponding with better outcomes. We have adjusting the scoring algorithm instead to be: $100 * (\text{raw score} - \text{lowest possible score}) / \text{score range}$. This calculation results in higher scores corresponding to better outcomes and an overall scale of 0-100.

Additionally, it was observed that the scoring of the OAB-SAT-q Endorsement subscale could have unintended behavior when dealing with missing data. The range of possible responses for component questions 9 and 10 (1 through 4) is different from the range of possible responses for component question 11 (1 through 6), so if any question is missing, the range of possible values for the imputed value of the missing response does not match the range of the original question. For example, if $Q9=4$, $Q10=\text{Missing}$, and $Q11=6$, then the imputed value for $Q10$ is 5, which is outside of the 1-4 range possible for $Q10$. This further causes problems when transforming the score as the transformed score can exceed 100. From the example provided, the transformed score is $100 * (\text{sum}(4,5,6) - 3) / 11 = 109.09$.

We have adjusted the missing value handling instead to be: average the non-missing responses as proportions of their maximum possible values (divide each non-missing response by its maximum possible value) and then scaling that average against the maximum possible value of the missing response. For example, if $Q9=4$, $Q10=\text{Missing}$, and $Q11=6$, then the imputed value for question 10 is as follows $[(4/4 + 6/6)/2] * 4 = 4$ and the transformed Endorsement score is $100 * (\text{sum}(4,4,6) - 3) / 11 = 100$, so the score does not exceed 100.

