OAB-SAT-q Side Effects Score at 12 Months	Continuous	The OAB-SAT-q Side Effects Score will be computed at 12 months (and 3 and 6 months) using the standard scoring algorithm. Specifically, if the response to question 5 is Never then the score is 100, regardless of the responses to questions 6 and 7. If the response to question 5 is not Never, then sum the responses across questions 5 (reverse coded: 1=All of the time, ..., 5=A little of the time), 6 (1=Extremely bothersome, ..., 5=Not at all bothersome), and 7 (1=A great deal, ..., 7=Not at all), then subtract from the maximum possible sum score (15) and divide by the range of possible scores $(15-3=12)$, then multiply by 100. If less than half of the responses are missing, then the score will be calculated by substituting the missing responses with the average of the non-missing responses, otherwise no score is calculated. If data for an assessment time point are missing, the outcome variable will be coded as missing.

Network

Protocol ESTEEM Statistical Analysis Plan

Variable	Type	Definition
OAB-SAT-q Endorsement Score at 12 Months	Continuous	
The OAB-SAT-q Endorsement Score will be computed at 12 months (and 3 and 6 months) using the standard scoring algorithm. Specifically, instructions are to sum responses across questions 9 (1=Definitely would not use the same treatment again, ..., 4=Definitely would use the same treatment again), 10 (1=Definitely would not recommend, ..., 4=Definitely would recommend), and 11 (1=Extremely Dissatisfied, ..., 6=Extremely Satisfied), then subtract from the maximum possible sum score (14) and divide by the range of possible scores (14-3=11), then multiply by 100. If less than half of the responses are missing, then the score will be calculated by substituting the missing responses with the average of the non-missing responses, otherwise no score is calculated. If data for an assessment time point are missing, the outcome variable will be coded as missing.

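### The SAP's new rule for a missing OAB-SAT-q Endorsement item scales by the item maximum although items start at 1, so it still gives impossible and distorted scores

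*SAP*

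**What the plan says.** The Endorsement subscale sums three items. SAP 9.5.1 gives questions 9 and 10 a range of 1 to 4 and question 11 a range of 1 to 6, so the raw sum runs from 3 to 14. An item is imputed only when fewer than half are missing (SAP 9.2, Endorsement row), which here means exactly one of three.

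SAP 9.5.1 makes two changes to the published scoring:

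- **Direction.** The score becomes 100 × (raw - lowest)/range, so that higher is better, with an "overall scale of 0-100".
- **Missing item.** Substituting the mean of the answered items can give a value the item cannot take. The SAP's example is Q9 = 4, Q10 missing, Q11 = 6, which imputes 5 and scores 109.09. The replacement is to "average the non-missing responses as proportions of their maximum possible values", then multiply that average by the missing item's maximum. The same example then imputes 4 and scores 100.

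The Endorsement row of SAP 9.2 was not updated. After summing the items it still says "then subtract from the maximum possible sum score (14) and divide by the range of possible scores (14-3=11", and it still fills a missing item with the plain mean of the others.

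**The concern.** Dividing by the maximum puts items on a common scale only if they all start at 0. These start at 1, so the worst answer becomes 1/4 on questions 9 and 10 but 1/6 on question 11. The rescaled items agree at the top and disagree everywhere below it. The only worked example in the SAP is at the top, where the fault cannot show.

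Two things are at stake. First, the rule was changed because imputed values left the item's range, and followed exactly it still produces such values. It also gives different scores to women with equally bad answers, depending on which item is blank. Second, a programmer working from the variable table in SAP 9.2 would produce a reversed scale and apply the discarded missing-item rule.

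**Working it through.** **Inputs.** Q9 and Q10 range 1–4, Q11 range 1–6, and score = 100 × (sum - 3)/11 (SAP 9.5.1, with the range of 11 also in SAP 9.2). One item is missing.

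**The SAP's own example (4, missing, 6).**
- Old rule: imputed (4 + 6)/2 = 5; score 100 × (15 - 3)/11 = 109.09. Reproduced.
- New rule: imputed [(4/4 + 6/6)/2] × 4 = 4; score 100 × (14 - 3)/11 = 100. Reproduced.

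**New rule at the bottom of the scale.**
- Q9 = 1, Q11 = 1, Q10 missing: imputed [(1/4 + 1/6)/2] × 4 = 0.833, below the minimum of 1. Score 100 × (2.833 - 3)/11 = -1.52.
- Q9 = Q10 = 1, Q11 missing: imputed [(1/4 + 1/4)/2] × 6 = 1.5. Score 100 × (3.5 - 3)/11 = 4.55.

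Both women gave the worst answer to every item they completed, yet their scores differ by 4.55 + 1.52 = 6.07 points (6.06 unrounded). Under the old rule both imputed values are 1 and both scores are 0, so the floor error is new.

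**Comparator.** Range-based scaling imputes 1 + m × (M - 1), where m is the mean of (response - 1)/(maximum - 1) over the answered items and M is the missing item's maximum.

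**Error of the new rule against the comparator.**
- Q10 missing (Q9 is the same by symmetry). New rule: Q9/2 + Q11/3. Comparator: 0.2 + Q9/2 + 0.3 × Q11. Difference: (Q11 - 6)/30. At Q11 = 1 this is -5/30, or -1.52 score points. At the midpoint Q11 = 3.5 it is -2.5/30, or -0.76 points.
- Q11 missing. With S = Q9 + Q10, new rule: 0.75 × S. Comparator: 5S/6 - 2/3. Difference: 2/3 - S/12. At S = 2 this is 0.5, or +4.55 points. At the midpoint S = 5 it is 0.25, or +2.27 points.

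**Enumeration of all patterns with one item missing.**

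| Missing item | Patterns | Imputed range | Score range | Scores outside 0–100 | Error, range | Error, mean |
|---|---|---|---|---|---|---|
| Q9 | 24 | 0.83 to 4 | -1.52 to 100 | 1 | -1.52 to 0 | -0.76 |
| Q10 | 24 | 0.83 to 4 | -1.52 to 100 | 1 | -1.52 to 0 | -0.76 |
| Q11 | 16 | 1.5 to 6 | 4.55 to 100 | 0 | 0 to +4.55 | +2.27 |

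The means weight every pattern equally. The error is zero only when Q11 = 6 (Q9 or Q10 missing) or when Q9 = Q10 = 4 (Q11 missing).

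**SAP 9.2 against SAP 9.5.1.** For a woman with the best answers (sum 14), the Section 9.2 formula gives 100 × (14 - 14)/11 = 0, while the Section 9.5.1 formula gives 100 × (14 - 3)/11 = 100. The Satisfaction, Side Effects and Convenience rows carry the same reversed formula. The Side Effects row contradicts itself: a woman who never has side effects scores 100, while the best raw total otherwise (15) scores 100 × (15 - 15)/12 = 0.

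**The case against.** The strongest reply is that the new rule is a real improvement and does what its example was meant to show: no score exceeds 100. By the same yardstick and equal weighting, the old rule was much worse. With Q11 missing its error was -(S - 2)/3 item points, which is -18.2 score points at S = 8 and -9.1 on average. With Q9 or Q10 missing it was 0.2 × (Q11 - 1), or +4.5 points on average. That stands, but a better rule can still be wrong. The SAP's stated reason was the mismatch with the item's own range, and that mismatch remains.

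It can also be said that the errors are measured against a chosen comparator, and that equal-weight averages are not the errors to expect in this trial because the documents give no response distribution. Both are fair. They do not touch the impossible values: an imputed 0.83 on a 1–4 item and a score of -1.5 are wrong under any comparator.

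Nothing suggests that item-level missingness differs between arms, so no bias in the treatment comparison is shown, and none is claimed. The distortion is in individual scores.

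On SAP 9.2, a careful reader is told which formula governs: Section 9.5.1 says it replaces the manual's derivation, and the version 2.1 change summary points there. The risk of a reversed scale is therefore limited to someone who programs from the table alone.

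**Conclusion.** The concern holds. Followed exactly, the rule in SAP 9.5.1 gives a score of -1.5 in two response patterns (one with Q9 missing, one with Q10 missing). It gives 4.5 instead of 0 for all-worst answers with Q11 missing, and it distorts most other patterns by smaller amounts: downward when Q9 or Q10 is missing, upward when Q11 is. The largest error is 4.5 points on a 0–100 scale. The error sizes assume that position within the item's range is the right basis for imputation, and the averages assume equally likely patterns.

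The practical weight is small. This is one subscale of an exploratory outcome, only women with exactly one Endorsement item missing are affected, and the documents do not say how many there are. The primary and secondary UDI analyses are unaffected. The outdated rows in SAP 9.2 are a separate, easily removed source of error.

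**What to change.** In SAP 9.5.1, replace the missing-item rule with this: average (response - 1)/(maximum - 1) over the answered items, then set the missing item to 1 + average × (maximum - 1), using the missing item's own maximum. The SAP's example still imputes 4 and scores 100. All-worst answers score 0 whichever item is missing, and all 64 patterns (24 + 24 + 16) fall within 0–100. Add a bottom-of-scale example beside the existing one.

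In SAP 9.2, put 100 × (raw - lowest)/range into the Satisfaction, Side Effects, Endorsement and Convenience rows, and have the Endorsement row refer to the corrected missing-item rule.

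The cost is one line of text and code for the rule and an edit to four table rows. If the scores have already been derived, rerun the Endorsement score and state how many women had an item imputed.

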9.5.2 Time-to-Failure

Although our primary outcome is at 12 months, the team was interested in whether perioperative BPTx may be associated with a delayed time to failure compared to Control. In other words, is BPTx associated with a significant effect, but the effect is not sustained at the 12-month time point? For example, if BPTx could delay the need for anti-muscarinics for up

to 9 months, this would be relevant information for counseling women and perhaps clinically recommending perioperative BPTx. As described previously, failure will be defined as initiation of any additional treatment for either SUI or UUI/OAB symptoms.

A class of survival model which can account for interval censoring (outcomes measured at pre-planned time points as opposed to continuously over time) will be used to determine if combined MUS+BPTx is associated with a decrease time to failure compared to MUS alone between 3-12 months. Depending on the distribution of the observed data, an accelerated failure time frailty model or a Bayesian survival model may be used. The model will be adjusted for the design effects of stratification by center and by baseline urge IE group.

9.5.3 Predictors of Treatment Success and Failure

Regression models will be created to identify predictors of change from baseline to 1 year for UDI total score and stress and irritative subscale scores. Participants who request additional treatment prior to 1 year will not be included in the predictive models. Potential predictors will include age, diary parameters such as number of UUI episodes/3 days, functional bladder capacity, bother severity at baseline. The relationship between potential predictors and outcomes will be explored in models that include one predictor plus stratification factors (center and baseline urge IE group). Predictive models will be constructed using backward selection of predictors. The impact of collinearity between predictors will be assessed and the final model modified as necessary.

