2.10. Innovation

[figure not shown]
This proposal is innovative for several reasons. First, it studies a population of women who are often excluded from clinical intervention trials but are at high risk for failing segregated SUI and UUI treatments. Second, in contrast to the historical paradigm of initiating treatments separately and stepwise for SUI and UUI, we will evaluate the effect of a combined surgical and non-surgical approach to optimize treatment outcomes. Third, this study will provide critical information regarding OAB outcomes after MUS and will be

powered to allow reporting of OAB and SUI outcomes separately after treatment. Finally, we will gain important predictive information regarding which patients may experience improvement, worsening, or no change in their OAB symptoms. At the completion of this study, we will understand whether a combined behavioral/surgical treatment approach is superior to surgery alone and will have predictive information that will be directly applicable to the clinical care of patients with this challenging condition.

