The overarching goal of ESTEEM is to evaluate the effect of combined treatment on improving both SUI and UUI outcomes in women with MUI. Therefore, any request for additional treatment for any lower urinary tract symptoms (SUI, UUI/OAB, voiding dysfunction) before the 1 year outcome for either of these symptoms will be considered treatment failure. The team agreed it would be difficult to withhold additional treatment from either group for the 1 year study duration; however, any additional treatment should be initiated after the acute postoperative recovery period. Clinically, some women may experience immediate

exacerbation of OAB symptoms after MUS followed by improvement, whereas other women may experience initial improvement but then recurrence of OAB symptoms several months later. Therefore, the team came to a consensus that any additional treatment should be deferred until 3 months postoperatively when OAB symptoms would be expected to have reached a baseline. This will allow enough time for complete physical and tissue recovery from the surgical procedure, will allow for assessment of potential BPTx early benefits, and will provide information on the natural course of OAB symptoms in the early postoperative period which is important for clinical counseling and decision-making. Any subjects receiving additional treatment prior to the 3 month time point will be considered a protocol deviation.

In the event that a randomized participant decides not to undergo surgery but then later changes her mind and has MUS surgery, the surgery will be considered additional treatment. For purposes of calculating follow up windows, the date of the original planned surgery that did not occur will be Time 0.

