The team discussed the issue of whether bladder capacity should determine eligibility. Historically, some clinicians have used bladder capacity as a criteria for whether a woman with MUI is eligible for an anti-incontinence procedure for SUI, often excluding women with capacities <150-200 cc to avoid exacerbation of OAB symptoms. Upon review of the literature, there is very little evidence to support excluding women with a "small" bladder capacity, or to guide what volume defines a "small" capacity bladder. Gamble et al performed a retrospective study to evaluate predictors of persistent postoperative detrusor overactivity after a variety of slings.⁷⁹ They found that the mean maximum cystometric capacity was smaller in women with postoperative persistent DO compared to those with resolved DO. However, the mean capacity in women with persistent DO was 459 cc (SD 185) versus 539 cc (SD 176), which does not support the traditional teaching of avoiding slings in women with capacities less than 150-200 cc. Also, 37% of their study population included traditional bladder neck slings, which may be more obstructive than MUS. Finally, the proportion of women reporting UUI *symptoms* in this study was not different between women who had resolved versus persistent DO, highlighting the limitation of using UDE parameters to predict symptoms. Numerous other studies have failed to demonstrate any specific bladder capacity cutoff that is associated with better or worse outcomes or poses a safety issue for MUS.

Because there is a lack of evidence to support setting a minimum bladder capacity cutoff for this study, women determined to be eligible for a MUS based on their clinician's judgment will be eligible for ESTEEM, regardless of bladder capacity. One advantage of the ESTEEM design is that only women who have been offered a MUS by their clinician will be eligible. Therefore, if the provider determines that the patient is not clinically a candidate for a MUS, she will not be eligible. In addition, we will be excluding women with a history of painful bladder or chronic pelvic pain syndromes who often have "small" capacity bladders. To further contribute to the literature about this issue, we will collect data on both maximum cystometric capacity on UDE and functional bladder capacity based on voiding diaries and evaluate these variables as potential predictors of worsening OAB symptoms in our exploratory analyses.

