4. Any concomitant native tissue procedures must be declared prior to randomization. Per exclusion criteria, women clinically requiring anterior vaginal prolapse or apical repairs are ineligible.
5. Tensioning of the sling will be performed in a fashion to ensure that it is a tension-free technique. This can include either by placing a blunt instrument between the sling and the urethra, or by folding a small knuckle of mesh in a Babcock clamp or similar method during tensioning.

5.1.c. Need for postoperative sling revision:

To address the issue of postoperative sling revision, the team developed a plan for several potential scenarios which may require the surgeon to revise the sling, detailed below. Women who undergo a sling revision will all be considered as having "additional treatment" in outcome analyses regardless of indication. Prior to sling revision, subjects will complete all outcome assessments including the primary outcome (UDI).

1. Urinary retention / incomplete bladder emptying (abnormal PVR) – An abnormal post-void residual is defined as PVR > 150 cc in this protocol (consistent with exclusion criteria). This is a known complication after MUS, and there is no evidence to support that this would be higher in women with MUI. Based on Barber's trial which included 70% women with MUI, the sling revision rate was 0-1%, which is also consistent with the TOMUS trial. For retention/incomplete emptying, the postoperative management and need for sling revision will be left up to the surgeon's clinical judgment.

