5.5.2. Postoperative visits and procedures

Patients will undergo clinical and PRO assessments at 3 months, 6 months, and 12 months postoperatively. (See Table 11 above). The primary outcome will be at 12 months. Additional treatment for patients with persistent OAB symptoms should not be offered in the first 3 months, given this time period may still represent recovery from acute events related to surgery. Patients requesting additional treatment in the first 12 months will be considered treatment failures, and will complete PRO assessments at the time of initiation of additional treatment. Any additional long term follow up beyond 12 months, consideration would need to be given to the natural history of progression and remission of OAB.^{112, 113}

Table 11. Timeline of visits, events, and data collection

	Baseline	Random-ization visit (T1-5 wks preop)	Preop BTPx visit (range 1-5 wks preop)	Surg MUS (T0)	Call (2-4d post-op)	2 wk post-Clinic	4 & 6 wks post	8 wk post-	3 mo post-Clinic and QoL	6 mo post-Clinic and QoL	12 mo post-Clinic and QoL
Estimated duration of clinic and/or BTPx visit for each group		Both: 1.5-2hr	Control: N/A Interv: 1.5hr		Contr: N/A Interv: 15 min	Control: 1.5hr Interv: 2.5hr	Control: N/A Interv: 1hr	Control: 1hr Interv: 2hr	Both: 1.5hr	Control: 1.5hr Interv: 2.5 hr	Both: 1.5-2hr
All subjects											
Consent	X										
Coordinator visit	X	X				X		X	X	X	X
Masked clinical staff visit (for PFM measures)		X				X		X			X
Hx/PE (update)						X		X	X	X	X
Medication audit	X					X		X	X	X	X
UDE	X										
UDI (inclusion and primary outcome)	X								X	X	X
Other PRO questionnaires		X							X	X	X
Voiding diary	X*					X*	X	X*		X*	X*
PFM measures		X				X		X			X
Additional treatment**						X	X (both groups by phone)	X	X	X	X
Adverse events				X		X	X (both groups by phone)	X	X	X	X
Voiding function (PVR)	X					X					
Subjects randomized to intervention only											
BTPx visit			X			X	X	X		X	
BTPx self-efficacy questionnaire		X								X	X
BTPx Adherence / Barrier questionnaire						X	X	X		X	X

* Data will be keyed into iMedidata

**For subjects who request/initiate additional treatment, all outcome measures will be completed prior to initiation of additional treatment.

6. Statistical considerations

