7.3 Handling of Dropouts and Missing Data

Missing data mechanisms will be explored, and sensitivity analyses will be conducted on primary outcomes to assess the robustness of the described analyses. Methods employed for sensitivity analyses may include multiple imputation or inverse probability weighting methodology. Imputation is not planned for secondary analyses. For further details on sensitivity analyses involving missing data see Attachment 16.2.

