9.3 Primary Analysis Methods

The mean change from baseline in UDI scores will be compared between groups at 1 year. As explained previously, participants will be permitted to seek additional treatment for SUI and/or OAB after 3 months following MUS. Because such treatment is expected to impact the participant's UDI score at 1 year, we will use an analysis method that accounts for the impact of additional treatment. Specifically, a general linear mixed model will be constructed to model change from baseline in UDI scores using scores recorded at time points up to 1 year following MUS. For participants who request additional treatment, only UDI measurements up to the time of additional treatment will be included in the model, and measurements taken between additional treatment and 1 year will be considered missing for the purpose of the primary analysis. The model will include fixed effects for treatment group, time, request for additional treatment, and interactions between those variables. It will also be adjusted for the design effects of stratification by center and by baseline urge IE group. Thus, the models will allow for different trajectories of change for women who are or are not randomized to BPTx and for those who do or do not request additional treatment. A statistical test based on the model will be conducted to assess whether mean changes from baseline in UDI scores at 1 year are significantly different between the two treatment groups, accounting for the percent of women in each group who request additional treatment. Sensitivity analysis will be conducted to test the robustness of test results to model specifications.

We will report whether change in total UDI score between baseline and one year is significantly different in the two groups. If the difference is statistically significant, the potential clinical significance of the difference will be discussed. We recognize that our sample size would allow us to find a difference between groups that is statistically significant yet smaller than published MIDs for total UDI score for women with MUI. However, published MIDs were calculated based on populations that may be somewhat different from the one targeted for enrollment in ESTEEM, and a secondary aim of ESTEEM is to explore whether the true MID in this population differs from previously published values.

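### The exploratory predictor models drop every woman who requests additional treatment before 1 year, and no planned sensitivity analysis covers that selection

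*SAP*

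**What the plan says.** SAP 9.5.3 and protocol 6.2.3.c plan regression models for predictors of the change in UDI total, stress and irritative scores from baseline to 1 year. Listed predictors are age, diary parameters, functional bladder capacity and baseline bother. Both sections then state: "Participants who request additional treatment prior to 1 year will not be included in the predictive models".

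Elsewhere the documents treat the same women as follows.

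- Protocol 3.4.1.c says that a request for additional treatment "before the 1 year outcome for either of these symptoms will be considered treatment failure". Protocol 5.5.2 agrees: "Patients requesting additional treatment in the first 12 months will be considered treatment failures". SAP 16.1 defines failure by the start of additional treatment.
- SAP 9.3 keeps these women in the primary analysis: "For participants who request additional treatment, only UDI measurements up to the time of additional treatment will be included in the model". Protocol 3.4.1.c asks them to complete the outcome measures before additional treatment starts.
- On bladder capacity, the discussion after the exclusion criteria in protocol 4.3 says the team will "evaluate these variables as potential predictors of worsening OAB symptoms in our exploratory analyses". Yet protocol 5.1.c says "Women who undergo a sling revision will all be considered as having" additional treatment, whatever the indication, so a revision for worsening OAB removes the woman from the model.
- Protocol 2.10 sets the aim: "we will gain important predictive information regarding which patients may experience improvement, worsening, or no change in their OAB symptoms".

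**The concern.** A section on predictors of success and failure contains none of the women whom the plan itself calls failures. Leaving them out conditions on an event that is linked to the outcome. If requests depend on outcome alone, slopes shrink towards zero. If a predictor also affects requests directly (age might, if it affects willingness to ask; that is an assumption), its slope can move either way, and a predictor with no true effect can acquire one.

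No planned sensitivity analysis reaches these models. SAP 9.3 covers the specification of the primary model. SAP 7.3 and 16.2 cover missing data for the primary outcome and the dryness and MID indicators. SAP 9.5.1 covers the dichotomous voiding-frequency outcomes, and SAP 13 covers one site's data. The time-to-failure analysis in SAP 9.5.2 compares arms and does not relate baseline predictors to failure.

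At stake is what the trial tells clinicians about which women do poorly after a sling. That is one exploratory aim.

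**Working it through.** **Nearest stated figure.** The documents give no bias or power figure for these models. The sample size does reproduce: 200/0.85 = 235.3, rounded up to 236 per group, or 472 in total. That leaves about 400 evaluable women.

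**Share excluded.** SAP 6 assumed requests from 30% (MUS only) and 20% (MUS+BPTx), an average of 25%, or 100 of 400. SAP 13 later calls the number of failures relatively small but gives no count. I assume 5-10%, or 20-40 of 400.

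**Selection model (all inputs assumed; standardised, higher = worse).** Y is the 1-year change, X a predictor with correlation ρ to Y, and the request propensity is S = cY + bX + noise with variance 1. The top share p of S is excluded. With t = Φ⁻¹(1−p), λ = φ(t)/(1−p) and d = λ(λ+t), the slope among the women kept is

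[ρ − d(cρ+b)(c+bρ)] / [1 − d(cρ+b)²].

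At p = 5%: t = 1.645, λ = 0.109, d = 0.190. At p = 10%: t = 1.282, λ = 0.195, d = 0.288.

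**(a) Requests depend on outcome alone (b = 0).** The share of the slope retained is (1 − dc²)/(1 − dc²ρ²). For p = 10%, c = 0.5, ρ = 0.3: (1 − 0.072)/(1 − 0.0065) = 0.934. Over c 0.3-0.5 and ρ 0.2-0.4, 95-99% is retained at 5% and 93-98% at 10%. With c = 0.7 it would be 91-92% and 86-88%.

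**(b) The predictor also drives requests (c = 0.5).** For a null predictor (ρ = 0) the false slope is −dbc/(1 − db²). For p = 10%, b = 0.5: −0.072/(1 − 0.072) = −0.078. The false-positive rates come from 20,000 simulated samples of 400; a control run with b = 0 gave 4.9-5.2%.

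| | b = 0.2 | b = 0.3 | b = 0.5 |
|---|---|---|---|
| Null, 5% excluded | -0.02 | -0.03 | -0.05 |
| Null, 10% excluded | -0.03 | -0.04 | -0.08 |
| False positives at 0.05, 5% / 10% excluded | 7% / 9% | 9% / 14% | 17% / 31% |
| True +0.30, 5% / 10% excluded | 0.27 / 0.25 | 0.26 / 0.24 | 0.24 / 0.20 |
| True -0.30, 5% / 10% excluded | -0.30 / -0.31 | -0.31 / -0.32 | -0.33 / -0.35 |

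The standard error of a slope is about 1/√360 to 1/√380, or 0.05. If the planning SD of 50.4 for UDI total is taken as the SD of the change, -0.08 is 0.08 × 50.4 = 4.0 points per SD of the predictor.

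**(c) Scores at 3, 6 and 12 months.** Adjacent correlation is 0.6 and requests occur after month 3 or 6. The alternative is a mixed model that keeps every woman up to additional treatment, with predictor-by-time terms. The table shows a null predictor at 10% excluded.

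| Requests depend on | b | Requesters excluded | All women, mixed model | Bias removed |
|---|---|---|---|---|
| Last recorded score | 0.2 | -0.018 | 0.00 | all |
| Last recorded score | 0.5 | -0.045 | 0.00 | all |
| Half recorded, half 12-month score | 0.2 | -0.033 | -0.019 | 42% |
| Half recorded, half 12-month score | 0.5 | -0.080 | -0.044 | 45% |
| 12-month score only | 0.2 | -0.037 | -0.029 | 22% |
| 12-month score only | 0.5 | -0.091 | -0.071 | 22% |

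At 5% excluded in the half-and-half case, -0.020 becomes -0.011 and -0.050 becomes -0.027. For a true +0.30 in that case at 10%, exclusion gives 0.248 (b = 0.2) and 0.204 (b = 0.5); the mixed model gives 0.271 and 0.248. Full recovery in the first two rows is expected by construction, because those requests are missing at random.

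**The case against.** **The exclusion is deliberate and stated.** Both documents name the excluded women, and SAP 9.3 gives a reason that carries over: additional treatment is expected to change the 1-year UDI. Predicting change among women who had no further treatment is a legitimate target, and preferring another is partly a choice of estimand. This stands, and it is why the planned model should stay. But the reason supports discarding scores after additional treatment, not discarding the woman and her earlier scores.

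**Other provisions help.** SAP 9.5.6 studies baseline thresholds for success with no stated exclusion, and SAP 2 allows further exploratory analyses without an update. A reader might infer that 9.5.3 is the plan's only look at baseline predictors; it is not. Still, 9.5.6 does not estimate these slopes, and permission is not a plan. The sentence in SAP 7.3, "Imputation is not planned for secondary analyses", concerns secondary analyses and adds little for an exploratory one.

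**The size is assumed, and the larger figures use the harsher mechanism.** This stands. A woman asks for treatment before her 12-month score exists. If requests follow recorded scores, the false slope at 10% excluded is only about 0.3-0.9 standard errors.

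**Sling revisions are few.** Protocol 5.1.c cites 0-1% in earlier trials, in the context of retention; that is at most about 5 of 472 women. The example shows the logic but adds little to the size.

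**Conclusion.** The concern holds in a limited form. The models exclude the plan's own failures, the event is outcome-related, and no planned sensitivity analysis covers it. Under assumed 5-10% exclusion and outcome loadings of 0.3-0.5, slopes keep about 93-99% of their value if requests depend on outcome alone. With outcome loading 0.5 and predictor loadings 0.2-0.5, a null predictor gains a false slope of about -0.01 to -0.05 if requests follow recorded scores. The figure is about -0.02 to -0.08 if they depend on the 12-month outcome, and up to about -0.09 in the longitudinal set-up. The bias would be larger near the planned 25% rate or with stronger loadings.

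A reader might infer that the predictor results are seriously misleading, or that the planned model is an error to be replaced. The documents do not support either: they give no rate or selection strength, SAP 13 points to few failures, and the restricted population is declared. Nor does the point touch the primary or secondary treatment comparisons, which keep these women's scores up to additional treatment. Priority is low.

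**What to change.** Keep the 9.5.3 model and pre-specify a second one beside it: a longitudinal mixed model with all women, UDI scores up to additional treatment (the SAP 9.3 data rule) and predictor-by-time terms. Do not adjust for request status, since that conditions on the same event. Read the predictor effect at 12 months as the change expected without additional treatment. Report both models, and describe the requester-excluded results as applying only to women who did not request treatment.

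The cost is a few sentences in the SAP and one extra model; no new data are needed. If the planned models have already been run, the label and the added model remain feasible, with the timing stated.

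Three limits belong in the text. The added model relies on missing at random, which SAP 9.1 already assumes. It removes essentially all of the null-predictor bias if requests follow recorded scores, about 42-47% if half of the outcome part is unrecorded, and only about 22% if requests follow the 12-month score itself. And some pre-treatment scores may be missing, because women are asked for them but may not complete them.
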